**Table 7 Schedule of Procedures for End of Study Visit**

| Procedure                            | End of Study Visit
( $\pm$ 4 weeks) |
|--------------------------------------|--|
| Physical exam                        | X                                      |
| Pregnancy test                       | X                                      |
| Vital signs                          | X                                      |
| ECOG performance status              | X                                      |
| Serum chemistry                      | X                                      |
| Thyroid function tests               | X                                      |
| Hematology                           | X                                      |
| Urinalysis                           | X                                      |
| Concomitant medications a | X                                      |
| Assessment of AEs/SAEs a  | X                                      |
| Subsequent anticancer treatment      | X                                      |
| CCI [REDACTED]                       | [REDACTED]                             |
| [REDACTED]                           | [REDACTED]                             |

AE = adverse event; CCI [REDACTED] ECOG = Eastern Cooperative Oncology Group;

CCI [REDACTED]; SAE = serious adverse event.

a Concomitant medications and AEs/SAEs will be collected at this visit only.

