#### **4.1.6 Discontinuation of Investigational Product**

An individual subject in any of the treatment arms will not receive any further study drug if any of the following occur in the subject in question:

- 1 Withdrawal of consent
- 2 Any toxicity/AE that in the opinion of the investigator and/or the sponsor, warrants discontinuation of further dosing
- 3 Any AE that meets criteria for discontinuation as defined in the Toxicity Management Guidelines (see Section [3.1.3](#))
- 4 Pregnancy or intent to become pregnant (Section [5.6.2](#))
- 5 Delay of more than 56 days from the last administration of study drug to the next planned dose
- 6 Confirmation of disease progression (Section [4.3.1](#))
- 7 Unconfirmed disease progression and investigator determination that the subject is not eligible for a confirmation scan (Section [4.3.1](#))
- 8 Initiation of alternative anticancer therapy
- 9 Intercurrent illness or medical condition, in the judgment of the investigator and/or the sponsor warrants discontinuation of further dosing

Subjects who are permanently discontinued from receiving study treatment will be followed for protocol-specified assessments, including follow-up of any AEs, unless consent is withdrawn from further study participation (Section [4.1.5](#)), disease progression, the subject starts alternative treatment/clinical study, or the subject is lost to follow-up. All subjects will be followed for survival until the end of the study unless consent is withdrawn from further study participation.

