#### 4.2.2 Follow-up Period

**Table 6** presents follow-up procedures for subjects who completed study treatment and maintain DC, subjects who discontinued study treatment due to other reason not related to PD (Section 4.1.6), and subjects who experienced unconfirmed PD and are eligible for a confirmation scan. Procedures for subjects who discontinue study treatment due to PD are provided in Section 4.2.3. Overall, all subjects continuing in the study must adhere to the study procedures for up to 5 years (from randomization) provided they achieve DC and remain disease free.

As OS is a late endpoint in this patient population, after the planned 5-year post randomization study period, subjects may be contacted for survival every 12 months.

**Table 6 Schedule of Follow-up Procedures: Subjects Who Completed Study Treatment and Maintain DC, Subjects Who Discontinued Study Treatment Due to Other Reason Not Related to PD, and Subjects Who Experienced Unconfirmed PD and are Eligible for a Confirmation Scan**

| Time since Cycle 1 Day 1                    | ≤ 12 Months                          | > 12 to ≤ 24 Months               | > 24 to 60 Months             |
|---|--------------------------------------|-----------------------------------|-------------------------------|
| Follow-up based on previous scheduled visit | Every 8 Weeks
(± 3 days)          | Every 12 Weeks
(± 7 days)      | Every 6 Months
(± 4 weeks) |
| Procedure                            |                                      |                                   |                               |
| Physical examination                        | X                                    | X                                 | X                             |
| Vital signs                                 | X                                    | X                                 | X                             |
| ECOG performance status                     | X                                    | X                                 | X                             |
| Serum chemistry                             | X                                    | X                                 | X                             |
| Thyroid function tests a         | X                                    | X                                 | X                             |

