#### 4.2.3 End of Study

**Table 7** presents procedures for the end of study visit for all subjects. End of study visit will be performed when a subject discontinues study due to a confirmed PD, or a subject experienced an unconfirmed PD but is not eligible for a confirmation scan, or after 60 months of follow-up for subjects who achieve DC and remain disease free, or at the last study visit for subjects who discontinue study due to reason not related to PD.

Subjects who discontinue treatment due to any reason, including confirmed PD or initiation of alternative anticancer therapy, will be followed for survival according to the timepoints in **Table 6** (every 8 weeks up to 12 months post Cycle 1 Day 1, every 12 weeks from > 12 to ≤ 24 months, and every 6 months from > 24 to 60 months post Cycle 1 Day 1) unless the subject withdraws consent from further participation in the study. After 60 months, subjects may be contacted for survival every 12 months until the end of the entire study.

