#### **5.4.1 Time Period for Collection of Adverse Events**

AEs and SAEs will be collected from time of signature of informed consent up to 12 months post Cycle 1 Day 1, regardless of whether the subject discontinued treatment. Following the first 12 months post Cycle 1 Day 1, AEs and SAEs will be collected up to 3 months post last dose of study treatment, if applicable.

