### **3.6.1 Adverse Events and Serious Adverse Events**

Adverse events will be coded by Medical Dictionary for Regulatory Activities (MedDRA) version 26.0 and the type, incidence, CTCAE grade and relationship to study IP will be summarized. Specific adverse events will be counted once for each subject for calculating percentages. In addition, if the same adverse event occurs multiple times within a particular subject, the maximum CTCAE grade and level of relationship observed will be reported. If any associations of interest between adverse events and baseline characteristics are observed, additional stratified results may be presented.

Treatment-emergent adverse events (TEAEs) are defined as events present at baseline that worsen in intensity after administration of study IP or events absent at baseline that emerge after administration of study IP. All TEAEs that occurred on and after first dose up to 90 days after last dose of IP (any) will be summarized overall, as well as categorized by MedDRA System Organ Class and Preferred Term. In addition, all TEAEs with an onset date no more than 90 days after the last dose of IP (any) will be listed.

The AEs occurring from the signing of the informed consent and prior to the initiation of study IP will be listed.

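### For subjects who stop because of progression, the protocol's schedule ends AE collection at the end-of-study visit, while Section 5.4.1 continues it to 12 months or 3 months after the last dose

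*Protocol*

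**What the plan says.** Two sets of passages govern AE collection after treatment.

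**The collection period.** Protocol Section 5.4.1 collects AEs and SAEs from consent "up to 12 months post Cycle 1 Day 1, regardless of whether the subject discontinued treatment", and after that to 3 months past the last dose. Footnote b of Table 6 repeats this. Neither mentions progression. SAP Section 3.6.1 uses a matching limit: "All TEAEs that occurred on and after first dose up to 90 days after last dose of IP (any) will be summarized overall".

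**The visit schedule.** Table 6, which holds the AE row for follow-up, is titled for three groups: treatment completed with disease control, treatment stopped for a reason other than PD, and unconfirmed PD awaiting a scan. For the remainder, Section 4.2.2 states: "Procedures for subjects who discontinue study treatment due to PD are provided in Section 4.2.3". Section 4.2.3 then provides: "End of study visit will be performed when a subject discontinues study due to a confirmed PD", and the same visit serves unconfirmed PD not eligible for a confirmation scan. Table 7 gives the visit a window of 4 weeks either way, and its footnote a reads "Concomitant medications and AEs/SAEs will be collected at this visit only". What continues is survival: "Subjects who discontinue treatment due to any reason, including confirmed PD or initiation of alternative anticancer therapy, will be followed for survival".

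Two further sections support the schedule. Section 4.1.6 keeps subjects who are off treatment under assessment, "including follow-up of any AEs, unless consent is withdrawn from further study participation", but names disease progression among the other exceptions. Section 5.4.2 ends eCRF recording of AEs still unresolved at the end-of-study visit.

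**The concern.** A site with a subject who has stopped for confirmed PD cannot follow both sets of passages. One requires AEs to be collected for months more; the other provides no AE assessment after a single visit. Nothing says which prevails.

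This matters for the analysis because the length of AE observation would depend on progression, an outcome that treatment is meant to change. Safety is the first secondary objective listed, and SAP Section 3.6.1 reports AEs as percentages of subjects, with no allowance for unequal follow-up. SAP Section 3.6.2 adds immune-mediated events by outcome and time to onset, and both are sensitive to truncated collection. If a combination delays progression, the control arm would lose more post-dose observation, and AE percentages would differ partly because follow-up differs. The sponsor's own 3-month and 90-day limits show that it regards post-dose events as relevant.

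**Working it through.** The plan states no figure for this point, so there is none to reproduce. The check compares windows in days.

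**Inputs from the documents**
- Summary window: 90 days after last dose (SAP 3.6.1).
- End-of-study visit window: 28 days either way (Table 7).
- Collection period: to month 12 after Cycle 1 Day 1, or 3 months after last dose if later (5.4.1).

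**Assumption.** The gap *g* from last dose to discontinuation for PD is not stated. I use 0, 14 and 28 days (28 being one cycle), and 56 days, which is the limit on dose delay in Section 4.1.6.

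**Step 1: part of the 90-day window after the visit.** With *w* the visit's offset from discontinuation, uncovered days = 90 − max(0, *g* + *w*).

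| *g* (days) | *w* = −28 | *w* = 0 | *w* = +28 |
|---|---|---|---|
| 0 | 90 | 90 | 62 |
| 14 | 90 | 76 | 48 |
| 28 | 90 | 62 | 34 |
| 56 | 62 | 34 | 6 |

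For gaps of 0 to 28 days and a visit 0 to 28 days after discontinuation, 34 to 90 days are uncovered. With a 56-day gap and the same visit timing, the range is 6 to 34 days.

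**Step 2: what Section 5.4.1 would give.** Collection ends at max(12, *m* + 3) months for a last dose in month *m*.
- *m* = 2: ends at month 12, 10 months after last dose.
- *m* = 6: ends at month 12, 6 months after.
- *m* = 10: ends at month 13, 3 months after.
- *m* = 12: ends at month 15, 3 months after.

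Taking 3 months as about 90 days, the SAP window is always covered under Section 5.4.1, whatever the progression status.

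**Step 3: dependence on the progression rate (illustration only).** Assume exponential PFS with the 17.2-month durvalumab median cited in Protocol Section 1.1, and count every PFS event as progression. Then P(event by month 12) = 1 − exp(−ln 2 × 12 × HR / 17.2).
- HR 1 (control): 0.383, about 23 of 60.
- HR 0.5 (assumed): 0.215, about 13 of 60.

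If each such subject lost 34 to 90 days, the share of the arm's 90-day window lost would be:
- control: 0.383 × 34/90 = 0.145, up to 0.383;
- HR 0.5: 0.215 × 34/90 = 0.081, up to 0.215.

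This shows the direction of the dependence. It does not estimate its size, because PFS events include deaths, the median comes from another trial, and the hazard ratio is assumed.

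**The case against.** The strongest reply concerns timing. The amendment log (Section 9.1) places footnote a in Amendment 4, as a clarification, when no subject was on treatment any longer. A reader might infer that the footnote caused AEs to be lost during the trial. The documents do not support that: subjects who stopped treatment for PD did so before the footnote was added. This part of the reply stands. It does not remove the conflict, which also sits in the current text of Sections 4.1.6, 4.2.2 and 4.2.3. Without the footnote, these subjects would still have no scheduled AE assessment after the end-of-study visit.

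Other points also stand in part:
- AEs are assessed at every treatment cycle, and the open question in Section 5.4.4 looks back to the previous contact. The gap therefore begins only after the end-of-study visit.
- PD without clinical deterioration needs a confirmatory scan at least 4 weeks later (Section 4.3.1). If drug is held meanwhile, Table 6 applies and AEs are collected. A reader might infer that at most 4 weeks of the 90 days are ever observed. Step 1 shows 56 days (90 − 34) with a 28-day gap and a visit at +28, and 84 days (90 − 6) with a 56-day gap.
- Deaths not clearly due to progression remain reportable as SAEs through follow-up (Section 5.4.3). Section 5.5 requires reporting of SAEs arising during the study, and the sponsor may request more on ongoing events (Section 5.4.2).
- The SAP's 90 days limit which collected events are summarized and do not promise 90 days of follow-up. The direct contradiction is inside the protocol; the SAP only fails to allow for it.
- Safety analyses are descriptive, so no formal test is distorted.

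**Conclusion.** The contradiction is real, and no passage settles it. Following the schedule would make AE observation after the last dose depend on progression; following Section 5.4.1 would not.

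Under the schedule, about 34 to 90 of the 90 days are unobserved in a subject who stops for PD. This assumes 0 to 28 days from last dose to discontinuation and a visit 0 to 28 days later; a longer gap leaves less unobserved. The same mechanism applies to a subject who completes treatment and progresses within 90 days of the last dose. The loss concerns mainly non-fatal events and is larger in an arm with more progression.

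A reader might go further and infer that the safety comparison has been biased, or that some 38% of control subjects were affected. The documents support neither. They do not say which rule sites applied, and they give no AE or progression counts by arm. The 38% is the illustrative PFS-event proportion from Step 3. The primary endpoint is not touched. The point is worth correcting because the AE tables are hard to interpret without knowing which period was applied.

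**What to change.** **Protocol.** Reconcile Table 7 footnote a and Sections 4.1.6, 4.2.3 and 5.4.2 with Section 5.4.1, so that one AE period applies to all treated subjects, including those with confirmed PD. For any subject whose window is still open, ask about AEs at the survival contacts already scheduled. With treatment complete by Amendment 4, this may recover little, so the reporting changes matter more.

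**SAP and study report.**
- State which AE period was in fact applied to subjects who stopped for PD.
- Report actual AE follow-up after last dose by arm. SAP Section 3.3.1 summarizes duration of follow-up but does not specify this quantity.
- Add an exposure-adjusted AE summary, or one truncated at the collection period common to all subjects.

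**Cost.** Amendment wording, an AE question at contacts that already take place, and a few extra tables.

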### 4.3 Description of Study Procedures

#### 4.3.1 Efficacy

RECIST v1.1 (Eisenhauer et al, 2009; see [Appendix E](#)) will be used to assess subject response to treatment and allow calculation of PFS, ORR, and DoR, which will be performed according to the schedules in Section 4.2. Post-radiation changes which affect lesion sizes may occur and there may be high levels of necrosis/fibrosis with little or no active tumor in recently irradiated lesions. However, accepting these limitations in this patient population with prior curative radiation treatment, the prior irradiated lesions may be considered measurable and selected as target lesions providing they fulfill the other criteria for measurability. All images will be collected and stored for possible future central re-analysis. Additional disease assessments may be performed as clinically indicated.

Additionally, disease progression in the absence of clinical deterioration requires confirmation. The confirmatory scan should occur preferably at the next scheduled visit and no earlier than 4 weeks after the initial assessment of PD. Administration of study drug(s) may continue between the initial assessment of progression and confirmation for progression. Subjects with rapid tumor progression or with symptomatic progression that requires urgent medical intervention (eg, central nervous system metastasis, respiratory failure due to tumor

compression, spinal cord compression) will not be eligible to continue to receive study drug(s) neither will require a confirmatory scan.

CCI

CCI

- If progression is not confirmed, then the subject should continue study drug(s) and on treatment assessments.
- If repeat scans confirm progression, then the date of the initial scan should be declared as the date of progression.

Tumor assessments may include the following evaluations: cross-sectional imaging using computed tomography (CT) or magnetic resonance imaging (MRI) scan of the chest, abdomen, and brain.

- MRI (preferred) or CT scans of the brain will be performed at screening for all subjects
- CT or MRI scan of the chest and abdomen will be performed at screening and with each disease assessment for all subjects.

The preferred method of disease assessment is CT with contrast; if CT with contrast is contraindicated, CT without contrast is preferred over MRI. The preferred method for central nervous system imaging is MRI; if CT scan is performed, CT with contrast is required. The same method is preferred for all subsequent tumor assessments.

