## 4.8 Statistical Evaluation

### 4.8.1 General Considerations

Tabular summaries will be presented by treatment group. Categorical data will be summarized by the number and percentage of subjects in each category. Continuous variables will be summarized by descriptive statistics. Additional details of statistical analyses will be described in the statistical analysis plan.

The Intent-to-treat (ITT) Population includes all subjects who are randomized. Subjects will be analyzed according to their randomized treatment group.

The As-treated Population includes all subjects who receive any investigational product. Subjects will be analyzed according to the treatment they actually receive.

The Response-evaluable Population includes subjects from the As-treated Population who have a baseline disease assessment, have the opportunity to be followed for at least 16 weeks at the time of the DCO (ie, dosed at least 16 weeks prior to the time of the DCO), and either has at least one post-baseline disease assessment and/or discontinued treatment due to death or disease progression.

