- PFS, defined as the time from randomization until the first documentation of disease progression according to RECIST v1.1 or death due to any cause, whichever occurs first, regardless of whether the subject receives subsequent anticancer therapy prior to progression. Subjects who are alive progression free at the time of DCO will be censored on the date of their last evaluable tumor assessment. PFS-12 will be estimated using the Kaplan-Meier method.

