**Table 3.4.1      Summary of Censoring Guidelines for PFS**

Situation	Date of PD/Death or Censoring	PFS Outcome
Documented Progressive Disease (PD) or death	Date of earliest sign of PD or death, whichever comes first	Event (unless the censoring rule specified below)
Death or PD immediately after $\geq 2$ consecutive missed or non-evaluable disease assessments as per the protocol specified assessment schedule	Date of last progression-free disease assessment prior to missed or non-evaluable assessments, or randomization, whichever occurred last	Censored
No PD or death at time of analysis or lost to follow-up	Date of last evaluable progression-free disease assessment	Censored
No tumor assessment at baseline and no evidence of PD at first post-baseline disease assessment OR No tumor assessment post-first dose, and no death prior to second scheduled post-baseline disease assessment	Date of randomization	Censored

PD = progressive disease; PFS = progression-free survival.

Subjects having missing lesion data at baseline or no disease assessments post-first dose of IP will have PFS censored at the date of randomization unless the subject dies prior to the second scheduled post-baseline disease assessment in which case the death date will qualify as a PFS event.

If a subject has two or more consecutive completely missed or non-evaluable assessments followed immediately by death or an assessment showing radiologic disease progression, then the subject will be censored for PFS. PFS will be censored at the date of randomization or the last progression-free disease assessment prior to the missed or non-evaluable assessments, whichever occurred last.

If a subject has two or more consecutively missed or non-evaluable assessments followed by an assessment showing no radiologic disease progression, then the assumption will be that the subject did not progress during the missed or non-evaluable assessments.

The length of gap (in number of days) to determine two or more consecutive assessments is defined as the following:

- 126 days during the first 12 months (A 8-week disease assessment interval plus a 7-day window for each assessment).

- 182 days from month 12 to month 24 (A 12-week disease assessment interval plus a 7-day window for each assessment).
- 422 days after month 24 (A 6-month disease assessment interval plus a 4-week window for each assessment).

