Subjects remaining on study without radiologic disease progression or death at the time of analysis will be censored for PFS at the date of their last evaluable disease assessment.

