### 7.1.5 Assignment of Dates of Disease Progression or Disease Response

For all analyses of endpoints resulting from an application of RECIST v1.1 to investigator assessed tumor measurements, there may be cases in which disease assessments span a series of dates. For establishing the start date of a subsequently confirmed response in which the disease assessment spans multiple days, the date of response assigned will be the latest date of evaluations corresponding to the disease assessment. The date of latest evaluation will also be assigned for a mid-study assessment showing SD as the date assigned for the purposes of censoring duration of response, TTP and PFS.

The date of PD will be the first date at which any objective diagnostic test provides data indicating PD. Specifically, for RECIST v1.1 the date of PD will be the earliest of the following 3 evaluation dates:

- Date of PD as indicated by target lesions: If PD is triggered by a change in sum of diameters of target lesions, and the dates of evaluation of the target lesions vary for the same assessment, assign the first evaluation date among target lesions.
- Date of PD as indicated by non-target lesions: If the dates of evaluation of the non-target lesions vary for the same assessment, assign the first evaluation date for which any non-target lesion exhibits a status of Unequivocal Progression.
- Date of PD as indicated by new lesions: If multiple new lesions are identified and the dates of evaluation for the new lesions vary for the same assessment, assign the first evaluation date for which any new lesion is detected.

In scenarios where the Investigator disease response is either a response or PD and differs from that of the application of RECIST v1.1 to investigator assessed tumor measurements separate response and/or progression dates will be required. Determination of the start date of a subsequently confirmed response in which the disease assessment spans multiple days remains the same as described previously. Specifically, the date of response assigned will be the latest date of evaluations corresponding to the disease assessment. The date of PD will be the earliest date of evaluations corresponding to the disease assessment.

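### Clinically declared progression without a RECIST progression scan is censored, not counted, in PFS and DoR unless death follows soon enough, and no planned analysis checks the effect

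*Protocol*

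**What the plan says.** **Events.** Protocol Section 4.8.3 defines PFS as "the time from randomization until the first documentation of disease progression according to RECIST v1.1 or death due to any cause, whichever occurs first". SAP 3.4.2.4 agrees, and SAP 3.4.2.2 gives DoR the same progression, death and censoring dates. SAP 7.1.5 adds: "The date of PD will be the first date at which any objective diagnostic test provides data indicating PD". Neither document has an event, or a censoring row, for progression declared on clinical grounds.

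**At clinical progression.** Protocol 4.3.1 deals with "Subjects with rapid tumor progression or with symptomatic progression that requires urgent medical intervention" and says that they "will not be eligible to continue to receive study drug(s) neither will require a confirmatory scan". Extra disease assessments are permitted when clinically indicated but are not required. Scheduled assessments cover chest and abdomen; brain imaging is scheduled at screening only (Table 5).

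**Afterwards.** Protocol 4.1.6 ends protocol assessments at disease progression. Section 4.2.2 sends subjects who stop for PD to Section 4.2.3, that is, to the end-of-study visit and then survival contacts. Table 7 ("Schedule of Procedures for End of Study Visit") shows no scan row, although the scan rows in Tables 5 and 6 are legible.

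**Censoring.** Under SAP 3.4.2.4, subjects remaining on study "without radiologic disease progression or death at the time of analysis will be censored for PFS", at their last evaluable assessment. Table 3.4.1 censors at randomisation where there is "No tumor assessment post-first dose, and no death prior to second scheduled post-baseline disease assessment". A death that directly follows two or more consecutive missed assessments is censored back to the last progression-free assessment or randomisation, whichever is later.

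**The concern.** Kaplan-Meier, log-rank and Cox analyses assume that a censored subject has the same outlook as those still at risk. Here the censoring is triggered by the event of interest: a subject is judged to have progressed, scanning stops, and the subject is then treated as progression-free up to the last scan.

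The documents foresee such subjects. The Response-evaluable Population in Protocol 4.8.1 requires a baseline assessment and a subject who "either has at least one post-baseline disease assessment and/or discontinued treatment due to death or disease progression", so it admits someone who stopped for progression with no post-baseline scan.

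The analyses at stake are PFS, the PFS landmarks (12, 18, 24 and 36 months), the PFS subgroup forest plot and DoR. The study is open-label and the clinical call is the investigator's, so its frequency could differ between arms and move the hazard ratio in either direction. SAP 3.4.3 mentions investigator-reported outcomes without censoring rules, but it names no PFS analysis that counts clinical progression. Under SAP 7.1.3 the investigator visit response is itself derived from lesion data.

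**Working it through.** **1. The SAP's own gap figures.** SAP 3.4.2.4 defines two missed assessments as 126, 182 or 422 days. With gap = 2 × (scan interval + window):
- First 12 months: 2 × (56 + 7) = 126.
- Months 12 to 24: 2 × (84 + 7) = 182.
- After month 24: 2 × (183 + 28) = 422.

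All three reproduce.

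**2. What the rules do with each kind of subject.**

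| Subject | PFS outcome |
|---|---|
| Initial scan shows RECIST PD, no confirmatory scan | Event; the SAP does not require confirmation |
| Clinical progression after a clean week-8 scan (day 56), no further scan, death by day 56 + 126 = 182 | Event, at the death date |
| Same, death after day 182 | Censored at day 56 |
| Same, alive at analysis | Censored at day 56 |
| Clinical progression before any post-dose scan, death before the second scheduled scan (week 16, day 112) | Event, at the death date |
| Same, death later or alive at analysis | Censored at randomisation |

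DoR follows the same dates, but the last two rows cannot arise: a confirmed responder already has post-baseline scans.

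**3. Size: inputs.** From the documents: median PFS of 17.2 months (Protocol 1.1), the scan schedule of Tables 5 and 6, and the SAP's death and gap rules. Assumed, because the documents give no figure: exponential PFS, a 36-month cutoff, the share q of progressions that are clinical only, and median survival of 2 to 12 months after them.

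**4. Simple bound.** 12 × ln 2 / 17.2 = 0.4836, so true PFS-12 = exp(−0.4836) = 0.617. If every clinical-only progression were censored and none of these subjects died in time to count, the hazard would fall to (1 − q) of its value:
- q = 10%: exp(−0.9 × 0.4836) = 0.647, which is 3.0 points too high.
- q = 20%: exp(−0.8 × 0.4836) = 0.679, which is 6.2 points too high.

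This is a ceiling, because it ignores the death rules.

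**5. With the death rules.** Simulation of 200,000 subjects per scenario. Scan-detected progression is dated at the next scan, so the reference value is about 0.64 instead of 0.617.

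| q | Median survival after clinical PD | PFS-12, clinical PD counted | PFS-12, SAP rule | Overstatement (points) |
|---|---|---|---|---|
| 5% | 2 months | 0.639 | 0.645 | 0.6 |
| 5% | 12 months | 0.640 | 0.653 | 1.3 |
| 10% | 2 months | 0.639 | 0.651 | 1.2 |
| 10% | 12 months | 0.638 | 0.665 | 2.6 |
| 20% | 2 months | 0.636 | 0.661 | 2.5 |
| 20% | 12 months | 0.637 | 0.690 | 5.3 |

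Differences were taken before rounding. Repeat runs shift the upper ends by about 0.1 point, so the ranges are quoted as 0.6–1.3, 1.2–2.7 and 2.5–5.4.

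Among first-year clinical-only progressors, death still makes the subject an event in about 65% if median survival is 2 months, 42% at 4 months, 30% at 6 months and 16% at 12 months. Censoring at randomisation affects about 0.2% to 1.2% of all subjects.

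**6. Hazard ratio.** True HR 0.70, same death rules, survival 2 to 12 months, Monte Carlo error about 0.01:

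| Clinical-only share, control / experimental | Change in HR |
|---|---|
| 10% / 10% | less than 0.01 |
| 10% / 5% | up by about 0.01–0.03 |
| 15% / 5% | up by about 0.03–0.06 |
| 5% / 10% | down by about 0.01–0.03 |

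**The case against.** The best defence is that the group is narrower than it looks.

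- **The sentence in 4.3.1 waives only the confirmatory scan.** A reader might infer that these subjects need no scan at all and so never become events. The text does not say that. It follows a paragraph on the initial assessment of PD, and its examples (such as CNS metastasis or cord compression) are conditions that imaging would normally show. An imaged new lesion is PD. This stands. What remains is that a scan is optional, and that brain and spine lie outside the scheduled chest and abdomen imaging.
- **Early deaths are events.** A reader might infer that every clinical-only progressor is censored. Table 3.4.1 and its text do not support that; the fastest deaths are counted, though late, at the death date. This also stands, and it brings the bias below the ceiling in step 4.
- **The Response-evaluable contrast is not a contradiction.** SAP 3.2 excludes that population from the final analysis. It shows only that the case was foreseen.
- **Redaction.** Text directly after the quoted sentence and two rows of Table 7 are blacked out, so the handling in 4.3.1 cannot be read in full. The censoring rules in the SAP are legible and have no row for this case.
- **Low stakes.** PFS and DoR are secondary and the study was not sized for hypothesis tests. With 60 subjects, the standard error of PFS-12 is about √(0.617 × 0.383 / 60) = 0.063, ignoring censoring. Every bias above is smaller than that. This limits the importance; it does not make the censoring non-informative.

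**Conclusion.** The point holds in a limited form. Clinical progression without RECIST PD is censored under a stated rule, the censoring is informative, and no specified analysis shows how often it happens or what it does.

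The effect is modest: roughly 1 to 5 points on PFS-12 for shares of 5% to 20%, and about 0.01 to 0.06 on a hazard ratio of 0.70 under the unequal shares examined. Both rest on assumed shares and assumed survival.

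Three stronger readings are not supported. Primary ORR is not biased by this censoring, because such subjects stay in the ITT denominator. DoR cannot be censored at randomisation. Nothing in the documents shows that the share of clinical-only progressions differs by arm, and with equal shares the hazard ratio is nearly unchanged. The open-label design makes a difference possible, which is a reason to count these subjects, not evidence of bias. This is a cheap improvement to the secondary analyses and no threat to the main conclusion.

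**What to change.** Change SAP 3.4.2.2, 3.4.2.4 and Table 3.4.1 only:

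1. Keep RECIST-only PFS and DoR as the main analyses, and add a Table 3.4.1 row stating how progression without derived RECIST PD is handled.
2. Add one sensitivity analysis of PFS and DoR. Discontinuation of treatment or study for disease progression, without derived RECIST PD, becomes an event on the date of that decision. It should include subjects otherwise censored at randomisation (PFS only) and those whose later death is censored because scanning had stopped.
3. Report the number of such subjects per arm.

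The cost is some SAP wording and one extra table. SAP 3.3.1 already summarises reasons for treatment discontinuation and end of study, so no new data should be needed. If the counts are near zero, the table settles the matter.

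There are two limits. The added events rest on an unblinded investigator's judgement. Treatment lasts at most 12 months, and with a 17.2-month median about 62% of subjects are still progression-free then (0.617 above), so a later clinical progression is captured only if an end-of-study reason was recorded. No change to the imaging schedule is proposed: Protocol Amendment 4 records that all subjects have completed the treatment period.
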